**Validation of the Microarray Profiles (the “test set”): An independent set of 26 Revlimid® treated patients enrolled in the national trials patients was used to validate the microarray data (35).** A predictive analysis of the “test” set that including patients with del(5q) and those without del(5q) with known clinical outcomes, showed that the expression profile on pre-treatment marrow aspirates may be a useful tool in the clinical management of MDS patients. The ability to avoid potentially toxic side effects in patients unlikely to respond to Revlimid® would be of great benefit to the patients.

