### **5 Study Objectives and Endpoints**

#### **5.1 Objectives**

##### **5.1.1 Primary Objective**

To conduct a prospective trial testing the Revlimid® (lenalidomide) response signature in patients who have transfusion dependent, non-del(5q), low and intermediate-1 risk myelodysplastic syndromes (MDS) in order to confirm the predictive value of the signature and to establish the boundaries of the z-score which can be used to pre-select patients in future clinical studies.

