## 11 Biostatistical Analysis

### 11.1 Overview

The aim of the study is to compare the diagnostic ability of the gold standard microarray assay to the Luminex Bead assay and to quantitative real-time PCR assay in order to detect Revlimid®-response in patients with MDS. Earlier studies have shown microarray assay to identify responders with a sensitivity of 94% and a specificity of 86% (44). It is hypothesized that the less expensive and more clinically useful Luminex Bead assay will predict MDS Revlimid® responders with a sensitivity of 75% and a specificity of 70% compared to criterion gold standard microarray assay. However, it may be possible that real-time PCR will also be equally useful clinically and an easier assay to perform in the clinical lab setting as many pathology laboratories are now equipped with the necessary instrumentation. We will thus compare both the Luminex and real-time PCR assays, assuming the same level of sensitivity and specificity for each, to the gold standard microarray assay. These levels would be 80% of the sensitivity and specificity of the gold standard.

To test this hypothesis, a paired design will be used with each subject being tested with both diagnostic tests [microarray versus either Luminex or PCR; (written "Luminex" in the formula)]. The null hypothesis is that the difference in sensitivity rates will be more than 0.80, and the alternative hypothesis will be that the difference in rates will be less or equal to 0.80. Using the sample size formula:

$$n = \left( \frac{z_{(1-\beta)} + z_{(1-\alpha)}}{\log(\gamma/\delta)} \right)^2 \left( \frac{(\gamma+1)TPR(luminex) - 2(concordance\ probability)}{\gamma(TPR\ luminex)^2} \right)$$

Where  $1-\beta$  is the power (0.80) and  $\alpha$  is the Type I error rate (0.95),  $\delta$  is the percentage difference between the microarray assay true positive rate (TPR) and the luminex TPR. The concordance probability is the estimated percentage of both tests having concordant true positives. Using the estimated concordance of 50%, an estimated 100 subjects will be required. With concordance set at 60%, an estimated 59 subjects will be required. (Alonso, T Sample size calculations for comparative studies of medical tests for detecting presence of disease. Stats in medicine 2002; 21:835-852)

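### Section 11.1 hypothesises a sensitivity and a specificity for Luminex and PCR, but its only formal test and its sizing use true-positive rates

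*Combined protocol and SAP*

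**What the plan says.** The primary objective (5.1.1) is to confirm the signature's predictive value and to "establish the boundaries of the z-score which can be used to pre-select patients in future clinical studies". The end of section 4.8 gives the clinical purpose: "The ability to avoid potentially toxic side effects in patients unlikely to respond to Revlimid® would be of great benefit to the patients".

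Section 11.1 takes the microarray's sensitivity as 94% and specificity as 86%. It hypothesises that Luminex "will predict MDS Revlimid® responders with a sensitivity of 75% and a specificity of 70" per cent, and assumes the same for real-time PCR. On the size of both targets it says: "These levels would be 80% of the sensitivity and specificity of the gold standard".

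The section then sets out a paired design to test this hypothesis. It states: "The null hypothesis is that the difference in sensitivity rates will be more than 0.80". The alternative is the complement, a value at or below the same figure. In the formula, the rate is the Luminex true-positive rate (TPR), delta compares true-positive rates, and the concordance is that of true positives. Required numbers are given as 100 at 50% concordance and 59 at 60%.

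Sections 11.2 to 11.5 cover clinical response, sample storage, assay methods and safety. They contain no test, margin, interval or criterion for specificity.

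**The concern.** The hypothesis has two parts and the test addresses one. That matters more than usual here because no cut-off is fixed in advance. For any score, sensitivity can be raised as far as one likes by loosening the cut-off, and the price is paid in specificity. A criterion on sensitivity alone therefore puts no limit on how unselective an assay may be.

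The intended use is to select patients and spare likely non-responders a toxic drug. The share of non-responders spared is the specificity. A report that followed section 11.1 to the letter could present a favourable sensitivity comparison for an assay of little selective value, with no planned analysis to reveal it.

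**Working it through.** **Inputs.** From 11.1: microarray 0.94 and 0.86; Luminex and PCR 0.75 and 0.70; ratio 0.80; power 0.80; concordance 0.50 or 0.60. Planned total 56 (Synopsis). Response rates in the earlier non-del(5q) trial (4.7): 26% transfusion independence, 43% hematological improvement. Assumed: one-sided alpha 0.05 (printed as 0.95, but the formula uses z(1−α)); gamma = 1, meaning equal assays (no value is given); 0.80 read as a ratio.

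**1. The plan's own figures.** With c the concordance,

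n = ((z(0.80) + z(0.95)) / log(γ/δ))² × ((γ+1)·TPR − 2c) / (γ·TPR²).

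The first factor is (2.486/0.2231)² = 124.2.
- c = 0.50: 124.2 × 0.50/0.5625 = 110.4, so 111 (plan: 100).
- c = 0.60: 124.2 × 0.30/0.5625 = 66.2, so 67 (plan: 59).

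The stated figures are not reproduced from the stated inputs. Delta 0.79 would give 99 and 60. Nothing below depends on this. In every variant only true-positive terms enter.

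**2. The two targets.** 0.80 × 0.94 = 0.752 and 0.80 × 0.86 = 0.688, which match the hypothesised 75% and 70%. Both were derived as targets; only the first is tested.

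**3. What the sensitivity test lets through.** An always-positive assay has sensitivity 1 and specificity 0.
- As a ratio: 1/0.94 = 1.06, above 0.80.
- As a literal difference: 0.94 − 1.00 = −0.06, below 0.80.
- With a confidence bound: if the microarray finds x of 15 responders, the one-sided 95% lower bound for the ratio is exp[log(15/x) − 1.645·√((15−x)/(15x))]. Its minimum is 0.956, at x = 14, still above 0.80.
- Relative specificity: 0/0.86 = 0, which no planned analysis examines.

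**4. What this means for selection.** Take clinical response as the reference, with response rate p. Then PPV = p·Se / [p·Se + (1−p)(1−Sp)], and the share excluded is one minus the denominator.

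| Se / Sp | p = 26%: PPV, excluded | p = 43%: PPV, excluded |
|---|---|---|
| 75% / 70% | 0.195/0.417 = 47%, 58% | 0.3225/0.4935 = 65%, 51% |
| 95% / 10% | 0.247/0.913 = 27%, 9% | 0.4085/0.9215 = 44%, 8% |
| 100% / 0% | 26%, 0% | 43%, 0% |

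On relative sensitivity the second row (0.95/0.94 = 1.01) looks better than the first (0.75/0.94 = 0.80), although it selects almost nobody out.

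**5. Power if both measures were tested.** At 26%, 56 patients give 56 × 0.26 ≈ 15 responders and about 41 non-responders. Solving the same formula for power, with equal assays and a 0.80 margin:
- Sensitivity, rate 0.75, 15 responders, c = 0.50 to 0.60: 23% to 32%.
- Specificity, rate 0.70, 41 non-responders, concordant true negatives 0.50 to 0.65 (assumed; the documents give none): 47% to 94%.
- Both, if independent: 0.23 × 0.47 = 11% to 0.32 × 0.94 = 30%.

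If the true values are exactly those hypothesised, the ratios sit at the margin: 0.75/0.94 = 0.798 and 0.70/0.86 = 0.814. Using the microarray rate in the variance term, power is then about 5% for sensitivity (concordance 0.69–0.74) and about 7% for specificity (0.58–0.69). Joint power cannot exceed the smaller, about 5%.

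**The case against.** A reader might infer that a useless assay would be accepted under this plan. The documents do not support that. They contain no pass/fail or replacement rule for either measure. The primary endpoint in 5.2.1 is an assessment of the expression profile, the cut-off is meant for future studies, and 4.8 says only that Luminex may be adaptable. The always-positive assay is a limiting case. Section 4.8 reports that Luminex gave essentially the same results as the chips, and nothing suggests a specificity near 0% or 10%. What stands is that the one formal test cannot detect poor specificity, and no other analysis is specified that would.

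Sizing on sensitivity is defensible, since responders are the scarcer group (about 15 against 41). The missing analysis is the real gap.

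One might also say that specificity would surely be reported, given the stated aim of comparing diagnostic ability. Perhaps so, but section 11.2 specifies an exact interval for transfusion independence, and nothing comparable exists for specificity.

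Finally, the literal wording of the 0.80 as a difference is so lax that almost any assay meets it. That is a separate defect and also needs repair, but correcting it to a ratio would leave this gap in place.

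**Conclusion.** The point holds as an internal gap in 11.1: half of the stated hypothesis has no test, interval or criterion, and with the cut-off still open, sensitivity alone cannot show that Luminex or PCR is comparable to the microarray. This is structural and needs no assumed rates.

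The size does rest on assumptions. The PPV and exclusion figures take clinical response as the reference. Section 11.1 does not define a responder, hence the 26% and 43% columns, and its comparison with a gold-standard microarray leaves open whether the microarray call is the reference. An always-positive assay would have 100% sensitivity and 0% specificity either way.

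It would also be wrong to infer that a joint test could simply be added at little loss of power. With 56 patients, joint power is about 11–30% under favourable assumptions (equal assays, independence), and about 5% at most if the true values are exactly 75% and 70%.

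**What to change.** In section 11.1:

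1. Make specificity a co-equal measure. For Luminex and for PCR, each against the microarray, pre-specify paired estimates with confidence intervals for relative sensitivity among responders and relative specificity among non-responders.
2. Evaluate both at the same cut-off, and state how that cut-off is obtained.
3. State the reference (clinical response or microarray call) and define a responder.
4. State that an assay will be described as comparable to the microarray only if both measures support it, not on sensitivity alone.
5. If a formal joint test is kept, requiring both components to succeed needs no alpha split within one assay. State how the two assays are handled, and restate the power for both measures together with the assumed concordances.

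No new data are needed: every patient is already planned to have all three assays and a response evaluation. The cost is a little more analysis and a less favourable stated power. Settling the cut-off is a design decision and goes beyond wording.

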streptavidin-coated phycoerythrin, the labeled amplicons will be annealed to capture probe-linked fluorescent microspheres. Microspheres are detected by flow cytometry and captured labeled amplicons are quantified (Luminex) by subtracting background from the mean fluorescent intensity of each bead.

**Real-time PCR:** Total RNA from bone marrow mononuclear cells preserved in Trizol will be used for the Real-time PCR assay for the expression of 32 genes, which includes the 24 genes of interest and controls. Primers for each gene will be designed (Roche Biosystems) such that only the RNA transcript and no genomic DNA will be measured by the Roche Light Cycler quantitative PCR assay. The Sybergreen kit (Roche) which measures relative amount of gene specific transcript will be used. Results will be analyzed with the Roche Light Cycler analysis package.

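### Section 11.1's only formal assay comparison is paired sensitivity in responders; specificity has no test, and the continuous score in all 56 patients has no planned analysis

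*Combined protocol and SAP*

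**What the plan says.** The primary objective (5.1.1) is to confirm the signature's predictive value and "to establish the boundaries of the z-score which can be used to pre-select patients in future clinical studies". Section 4.10 has every patient's pre-therapy marrow studied by all three assays.

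Each assay gives a quantitative reading. Under 11.4, microarray values are RMA-normalised expression levels. For the bead assay, "captured labeled amplicons are quantified (Luminex) by subtracting background from the mean fluorescent intensity of each bead". The PCR kit "measures relative amount of gene specific transcript will be used".

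Section 11.1 assumes 94% sensitivity and 86% specificity for the microarray, and 75% and 70% for Luminex and for PCR. It describes the latter as 80% of the microarray's figures. The design is paired. The one stated hypothesis is on sensitivity: "The null hypothesis is that the difference in sensitivity rates will be more than 0.80". The sample-size formula contains only the true-positive rate and a concordance term, of which the plan says "The concordance probability is the estimated percentage of both tests having concordant true positives". Specificity appears as an assumed value and a target, with no hypothesis, test or sample size. Sections 11.1 to 11.4 specify no analysis of the z-score itself.

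**The concern.** True-positive rates are estimated from responders only. A comparison built on them leaves the non-responders, the larger part of the cohort, out of the one formal test of whether a simpler assay can stand in for the microarray. It also reduces a quantitative score to a positive or negative call, at boundaries that this trial is meant to establish.

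Two things are at stake. With so few responders, the sensitivity comparison may be unable to separate assays as different as the plan supposes, although data on all 56 patients will exist. And confirming that the score predicts response, which is part of the primary objective, has no test at all.

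**Working it through.** **1. How many patients the test uses.** Section 4.7 reports, for the earlier non-del(5q) trial, transfusion independence in 56 of 214 (26%) and hematological improvement in 92 of 214 (43%). Among 56 patients that is 56 × 56/214 = 14.7 and 56 × 92/214 = 24.1 responders. So 15 or 24 patients enter, and 41 or 32 do not. Section 11.1 does not say which definition of response applies, so both are carried through.

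**2. The plan's own figures.** "Using the sample size formula", the plan says, and reports 100 subjects at concordance 50% and 59 at 60%. Gamma is neither defined nor given a value. The text says alpha "is the Type I error rate (0.95", read here as one-sided 0.05, and that 1−β "is the power (0.80) and" so on. With γ = 1, δ = 0.80 and TPR = 0.75:

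- n = [(0.842 + 1.645)/ln(1/0.80)]² × (2 × 0.75 − 2c)/0.75² 
- c = 0.50: 124.2 × 0.889 = 110.4, so 111
- c = 0.60: 124.2 × 0.533 = 66.2, so 67

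The stated 100 and 59 are not reproduced. Values that the plan does not state come close: γ of about 1.013 to 1.015, or δ = 0.79 with γ = 1. On the same formula (γ = 1), 15 to 24 responders give power of 23–31% at c = 0.50 and 32–44% at c = 0.60, against the planned 80%.

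**3. Score model (assumed).** Equal-variance binormal scores matched to the plan's accuracies:

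- microarray: separation z(0.94) + z(0.86) = 2.635, AUC = Φ(2.635/√2) = 0.97
- Luminex or PCR: z(0.75) + z(0.70) = 1.199, AUC = Φ(1.199/√2) = 0.80

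**4. Why sensitivity alone does so badly.** If the calls are independent, a responder is discordant with probability 0.94 × 0.25 + 0.06 × 0.75 = 0.28, or 4.2 of 15. Exact McNemar needs at least six discordant pairs, all in one direction (2 × 0.5⁶ = 0.031; five give 0.0625). The asymptotic version rejects with four (4²/4 = 4 > 3.84), hence the gap between the two.

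**5. Power to detect the stated difference.** N = 56, two-sided 5%, complete data, 3,000 simulated trials per row:

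| Responders | Between-assay correlation | Exact McNemar | Asymptotic McNemar | Sensitivity + specificity calls, all 56 | Paired AUC (DeLong), all 56 |
|---|---|---|---|---|---|
| 15 | 0 | 7.5% | 27.5% | 62.6% | 71.8% |
| 15 | 0.3 | 5.6% | 29.3% | 69.6% | 78.7% |
| 15 | 0.6 | 5.7% | 31.8% | 78.6% | 90.4% |
| 24 | 0 | 26.8% | 44.0% | 69.8% | 80.8% |
| 24 | 0.3 | 26.7% | 49.3% | 76.3% | 88.6% |
| 24 | 0.6 | 29.3% | 57.9% | 85.5% | 95.8% |

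Over correlations 0.3 to 0.8, calls in all 56 reach about 70–88% (15 responders) and 76–94% (24), and the paired AUC about 80–97% and 89–99%. The continuous scale thus adds about 6 to 13 points beyond the calls.

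**6. Where the gain shrinks.**

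- Responder SD 1.5 times that of non-responders: the AUC adds nothing to about 2 points over the calls with 15 responders, and about 8 with 24.
- Only sensitivity differs (94% against 75%, specificity 86% for both): AUC 26–39% against asymptotic McNemar 26–30% with 15 responders; 34–50% against 43–59% with 24.
- Non-inferiority with truly equal assays, true-positive-rate ratio margin 0.80 and an AUC margin mapped from it: 30–47% on the ratio against 27–46% on AUC with 15 responders; 40–55% against 29–50% with 24.

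**7. Power to confirm that one 75%/70% assay predicts response.** With 15 responders: Fisher 84%, chi-square 88%, Mann-Whitney on the score 97%. With 24: 90%, 94% and 99%. With 15 responders and an SD ratio of 0.67 or 1.5, Mann-Whitney stays at 95–97% against Fisher at 83–84%.

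**The case against.** The strongest reply is that Section 11.1, though badly worded, seems to ask whether a simpler assay keeps 80% of the microarray's accuracy. That is a one-sided non-inferiority question on a ratio, and for it the AUC gives no gain (step 6). This stands, and it limits the power figures to the task of detecting a difference.

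Exact McNemar is not named in the plan, and the printed formula is a large-sample one. The fairer comparator at 15 responders is therefore about 30%, not 5–8%. This also stands.

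Pre-selecting patients depends on performance at a cut-off, which AUC does not describe. In the model above, AUC 0.80 fits 75%/70% and equally Φ(1.199 − 1.080) = 55% sensitivity at 86% specificity. This is a good reason to keep the sensitivity comparison.

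The cited signature paper may already supply a classification rule, since 94%/86% implies that one was used. The documents do not show it, so the cut-off cannot be called arbitrary. What can be said is that 5.1.1 leaves the boundaries to be established in this trial.

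None of this supplies the missing specificity test or the missing analysis of the score.

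**Conclusion.** The concern holds in a limited form. The only formal comparison uses 15 to 24 of 56 patients, specificity has no test, and the continuous score has no planned analysis although it is the subject of the primary objective. At the plan's accuracies and with 15 responders, power to detect the difference rises from about 30% (asymptotic McNemar) to about 70–88% when both kinds of call are used, and to about 80–97% with paired AUC. For confirming prediction, it rises from about 84% to 97%. The second result depends less on the model. All these figures assume binormal scores and complete assay and response data; the comparison figures also assume between-assay correlations of 0.3 to 0.8.

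A reader might infer more, in three ways that the documents do not support:

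- *Dichotomising throws away most of the power.* Most of the gain comes from admitting non-responders. The continuous scale adds about 6 to 13 points, less under unequal variances, and there is no consistent gain when only sensitivity differs.
- *Specificity is ignored.* It is named as a target; what is missing is its test.
- *AUC should replace the sensitivity comparison and carry the 80% tolerance.* That changes the quantity being compared. An AUC margin would be model-derived and would merge the sensitivity and specificity losses, and a simple DeLong limit at the mapped margin of about 0.17 rejected 8–10% of the time at a nominal 5%.

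**What to change.** In Section 11.1:

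1. Test each assay's prediction of response with its continuous z-score in all 56 patients, by Mann-Whitney or by logistic regression with the z-score as a linear term.
2. Add the paired AUC difference, microarray against Luminex and microarray against PCR, in all 56 patients, with a DeLong or paired-bootstrap 95% confidence interval.
3. Keep the paired sensitivity comparison at the chosen z-score boundary and add the matching specificity comparison, both with exact intervals.
4. Leave the 80% tolerance on sensitivity and specificity; do not restate it as an AUC margin.

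The cost is wording and a little analysis, with no extra patients, samples or assays. The AUC says nothing about performance at one cut-off, so item 3 must be reported beside it. These changes do not repair the separate faults in the sample-size paragraph (the printed alpha, the undefined gamma, the null worded as a difference), which need their own correction.

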### **Multi-institutional experience (MDS 002 and 003 trials):**

**Revlimid® in del(5q) patients:** The List experience described above was followed by a multicenter Phase II study (42) evaluating the efficacy of REVIMID® in transfusion dependent (TD)-MDS pts with del5q31. A multicenter Phase II trial (MDS 003) for transfusion dependent low to Int-1 del(5q) patients

showed remarkable results. Among 148 pts with del(5q31), 111 had this as an isolated cytogenetic abnormality, and 37 patients had additional chromosomal changes. The median age was 71 years (range, 37-95) with 66% females and 146 patients had a confirmed transfusion dependence. In an intent-to-treat analysis, transfusion independence was achieved in 99 patients (67%) with a median 5.3/dl hemoglobin increase (range: 1.1-11.4/dl). The median time to response was 4 weeks (range: 3.6-5.3 weeks). The transfusion independence rate was greater in patients with isolated del(5q) abnormality (69% versus 49%;  $p=0.003$ ). Cytogenetic response ( $\geq 50$  decrease in abnormal metaphases) was achieved in 70% of transfusion independent patients with 44% achieving a complete cytogenetic remission. Pathologic complete remission was documented in 32/110 (29%) evaluable patients. After a median follow-up of 9.3 months (range: 4.2 to 14.8+ months), the median response duration is not reached with only 10 responders (9%) failing.

**Revlimid® in non-del(5q) patients:** The results of Revlimid® treatment of transfusion dependant low to Int-1 patients without the del(5q) has also shown that Revlimid® is an effective treatment option (43). A total of 214 patients were treated with Revlimid® (MDS 002). Overall, 56 (26%) of 214 enrolled patients achieved transfusion independence. Median time to response was 5 weeks, median duration of response was 41.0 weeks (range, 8.0-136.4), and median Hgb increase achieved was 3.2 g/dL (range, 1.0-9.8). An additional 36 patients experienced a  $\geq 50\%$  reduction in RBC transfusions (hematological improvement in 92 [43%] patients). Of 47 (22%) patients who had an abnormal karyotype at baseline, 9 (19%) patients achieved a cytogenetic response (4 complete). These early findings indicate that Revlimid® has significant erythroid activity in patients with low- to int-1-risk MDS.

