### **5.2.2 Secondary Endpoints**

- Response will be evaluated **every 4 weeks during the first 12 weeks** of therapy for each of the 56 transfusion-dependent, non-del(5q) low/Int-1 risk MDS patients. Treatment will be stopped and the patient will be taken off the protocol in case of no response or stable disease by 12 weeks. International Working Group (**IWG 2006**) criteria will be used for response evaluation. The proportion of TI will be calculated and an exact 95% confidence interval of TI proportion will be estimated.
- The percent of major and minor responses in erythroid, platelets, neutrophils will also be calculated as the secondary endpoints.

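### The sample-size formula in 11.1 counts responders (or microarray-positive patients), not enrolled patients, so 56 patients do not give the stated 80% power

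*Combined protocol and SAP*

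**What the plan says.** Section 11.1 plans a paired comparison in which each patient is tested by microarray and by Luminex or real-time PCR. For the microarray it states: "Earlier studies have shown microarray assay to identify responders with a sensitivity of 94% and a specificity of 86% (44"). Luminex is hypothesized to reach 75% sensitivity and 70% specificity, measured against the microarray as gold standard. PCR is assumed to do the same. Of these levels the plan says: "These levels would be 80% of the sensitivity and specificity of the gold standard".

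The hypothesis is worded as a difference: "The null hypothesis is that the difference in sensitivity rates will be more than 0.80". The formula, however, uses log(gamma/delta). Power is 0.80 and the Type I error rate is printed as 0.95. Gamma is not defined. On concordance the section says: "The concordance probability is the estimated percentage of both tests having concordant true positives".

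Two results follow: "Using the estimated concordance of 50%, an estimated 100 subjects will be required", and "With concordance set at 60%, an estimated 59 subjects will be required".

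The synopsis sets the total at 56. Section 5.2.2 evaluates response "for each of the 56 transfusion-dependent, non-del(5q) low/Int-1 risk MDS patients", and 11.2 uses the same number. No section links 56 to 59 or 100, and none gives an expected response rate for sizing. The background (4.7) reports, for the earlier trial in non-del(5q) low/Int-1 patients: "Overall, 56 (26%) of 214 enrolled patients achieved transfusion independence". The same paragraph gives hematological improvement in 92 of 214 (43%).

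**The concern.** Sensitivity is a proportion of patients who are positive on the reference standard. A formula built only from sensitivities and joint true positives therefore returns a number of such patients. To get enrolment, that number must be divided by the share of enrolled patients who are reference-positive. The plan skips this step, calls the result subjects, and then fixes a total below either result.

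The paired comparison of sensitivities is the only quantity that the plan powers. If it rests on a few dozen responders at most, a Luminex or PCR comparison that misses its margin would be read against an 80% power that the stated inputs do not give.

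**Working it through.** **1. Reproducing 59 and 100.** With T the Luminex sensitivity and c the concordance, the printed formula is

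n = [(z_power + z_(1−alpha)) / log(gamma/delta)]² × [(gamma + 1)T − 2c] / (gamma T²).

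Inputs from 11.1: power 0.80 (z = 0.842), T = 0.75, delta = 0.80, c = 0.60 or 0.50. Assumptions: alpha is one-sided 0.05 (z = 1.645), replacing the printed 0.95, and gamma = 1.

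- First factor: (2.486 / 0.2231)² = 124.2.
- Second factor: (1.5 − 1.2)/0.5625 = 0.533 at c = 0.60; (1.5 − 1.0)/0.5625 = 0.889 at c = 0.50.
- Result: n = 66.2 and 110.4, that is 67 and 111, not 59 and 100.

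Taking alpha literally as 0.95 gives about 7 and 12. Several unstated input sets come close to the plan's figures:

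| gamma | delta | T | n at c = 0.60 | n at c = 0.50 |
|---|---|---|---|---|
| 1 | 0.79 | 0.75 | 59.3 | 98.9 |
| 1.01 | 0.80 | 0.74 | 59.1 | 100.3 |
| 0.96 | 0.76 | 0.76 | 59.2 | 100.0 |

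So 59 and 100 are plausible outputs of this formula, but the inputs used cannot be identified.

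**2. What n counts.** For two paired tests in n reference-positive patients with sensitivities gamma·T and T and joint positivity c, the discordant share is gamma·T + T − 2c. The large-sample variance of the log ratio of sensitivities is [(gamma + 1)T − 2c] / (gamma T² n). This is the second factor of the formula divided by n. A simulation in responders agrees: at delta 0.80, 67 responders (c = 0.60) give 79.9% power and 111 (c = 0.50) give 79.8%. Nor can c be a share of all patients if response is 26–43%, because 50–60% would exceed the response rate.

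**3. Responders among 56.** The rates in 4.7 are taken as assumptions: 56 × 0.26 = 14.6 and 56 × 0.43 = 24.1.

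**4. Power scaled from the plan's own figures.** If N reference-positive patients give 80% power, then n of them give Phi(2.486 × √(n/N) − 1.645). This needs no choice of gamma or delta.

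| Reference-positive patients | Against N = 59 | Against N = 100 |
|---|---|---|
| 14.6 (responders at 26%) | 34% | 24% |
| 24.1 (responders at 43%) | 48% | 34% |
| 19.5 (microarray-positive at 26%) | 41% | 29% |
| 27.1 (microarray-positive at 43%) | 52% | 36% |
| 56 (all patients counted) | 78% | 58.5% |

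The microarray-positive counts apply the plan's 94%/86% accuracy: 0.94 × 14.6 + 0.14 × 41.4 = 19.5 and 0.94 × 24.1 + 0.14 × 31.9 = 27.1.

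**5. Concordance against the stated sensitivities.** Joint positivity must lie between A + B − 1 and the smaller of A and B. For 0.94 and 0.75 this is 0.69 to 0.75, so 0.50 and 0.60 are both impossible. With both sensitivities at 0.75 the range is 0.50 to 0.75, and both values are possible.

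**6. Precision available.** The exact 95% confidence interval for sensitivity is 45–92% for 11/15 and 53–90% for 18/24. For a sensitivity ratio of 1 with both sensitivities 0.75, the approximate 95% interval is exp(±1.96 × √([1.5 − 2c]/0.5625/n)):

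- c = 0.60: 0.69–1.45 (n = 15) and 0.75–1.34 (n = 24).
- c = 0.50: 0.62–1.61 (n = 15) and 0.69–1.46 (n = 24).

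**The case against.** **The reference may be the microarray.** Section 11.1 describes the 75%/70% as accuracy against the microarray, which would make n a count of microarray-positive patients. The text does allow this reading, although it sits badly with a formula that compares two sensitivities and with the microarray's own 94% for responders. It softens the shortfall but does not remove it: those patients are still a subset of the 56.

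**The response rates are assumed, and others could be chosen.** This stands. The pilot in 4.7 reports 68% erythroid response with a normal karyotype and 17% with other abnormalities. At 68%, 56 patients give 38.1 responders and power of 64% against 59 and 46% against 100. The pilot was small (36 evaluable patients) and of a different case mix, so the larger trial in the matching population is the better guide. At no response rate can 56 patients supply 59 or 100 responders.

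**The gap between 56 and 59 is trivial.** Taken alone it is: 78% against 80%. The serious loss comes from the missing response-rate step or from the 50% concordance case.

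**The assay comparison is not the primary objective.** Section 5.1.1 names the predictive value of the signature and the z-score boundaries. The assay comparison is called the aim only in 11.1, and no decision rule for Luminex or PCR is given. So a reader should not infer that the trial cannot meet its primary objective, or that an assay would certainly be discarded wrongly. The documents support neither. Yet 11.1 is the plan's only sample-size argument, and it should be right.

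**Conclusion.** The point holds. In 11.1, n counts reference-positive patients, the plan reports it as subjects, and 56 is below both results and is not derived. This follows from the printed formula alone and is firm.

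The size is conditional. At 26–43% response, power scaled from the plan's own figures is about 34–48% (60% concordance) or 24–34% (50%). With microarray-positive patients as the denominator it is about 41–52% or 29–36%.

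Two stronger readings are tempting but not supported. One is that a particular low power has been established for this trial. It has not: the plan leaves gamma, delta, the reference standard and the response definition open, and other inputs would change the figure. The other is that the plan must have used delta 0.79. Other input sets fit 59 and 100 at least as well.

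Separately, the inputs need correction whichever denominator is meant: the Type I error rate of 0.95, the undefined gamma, the margin called a difference in a log-ratio formula, and concordances that cannot occur with sensitivities of 94% and 75%.

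**What to change.** Rewrite 11.1; no change to enrolment is required.

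1. State the reference standard (clinical response or microarray result) and that n counts patients positive on it. Withdraw the statement that 59 or 100 subjects suffice for 80% power.
2. Name the response definition that makes a patient a responder in this analysis. Give the expected number among 56 as an assumption: about 15 at 26%, about 24 at 43%.
3. State the resulting precision, for example the exact intervals for sensitivity in step 6. Report Luminex and PCR against microarray as a ratio of sensitivities with its 95% confidence interval.
4. If a test and a power statement are kept: correct alpha, state gamma and delta as ratios, use a concordance compatible with the sensitivities, and say whether 75% is the expected or the minimum acceptable sensitivity. Report power at the expected number of responders.

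The cost is a wording change and a less favourable power statement, with no added patients, visits or assays. Enlarging the study or dropping the formal test remain options for the sponsor, but this correction does not depend on either.
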